#### Best Overall Response:

The best overall response is determined once all the data for a subject is known. It is defined as the best response designation recorded between the date of first treatment and the date of objectively documented progression per RECIST v1.1 or the date of initiating subsequent therapy, whichever occurs first. For subjects without documented progression or subsequent therapy, all available response designations will contribute to the BOR assessment. The subjects best overall response assignment will depend on the findings of both target and non-target disease and will also take into consideration the appearance of new lesions.

#### Modifications to RECIST v1.1: Immune-related Response Criteria

Immune-related response criteria using uni-dimensional measurements are used to describe tumor shrinkage following RECIST-defined disease progression. The methodology is the same as described above for RECIST except:

1. New lesions do not automatically denote disease progression
2. The measurements of longest diameter of new measurable lesions are included in the sum of the measurements of the original target lesions.

Best immune-related responses, for subjects who have progression followed by tumor shrinkage are classified as irCR (disappearance of all lesions) or irPR ( $\geq 30\%$  reduction from baseline).

#### Continuation of treatment despite radiographic progressive disease

Patients who experience initial progressive disease may continue therapy if they are experiencing clinical benefit. The date of progression for calculation of PFS will remain the first CT scan that demonstrates progression (if it is confirmed on subsequent scan, as above).

For the subjects who continue nivolumab and ipilimumab study therapy beyond progression, further progression is defined as an additional 10% increase in tumor burden volume (relative to baseline) above the degree of progression identified at the time of initial PD. This includes an increase in the sum of diameters of all target lesions and/or the development of new measurable lesions.

New lesions are considered measureable at the time of initial progression if the longest diameter is at least 10 mm (except for pathological lymph nodes which must have a short axis of at least 15 mm). Any new lesion considered non-measurable at the time of initial progression may become measureable and therefore included in the tumor burden volume if the longest diameter increases to at least 10 mm (except for pathological lymph nodes which must have a short axis of at least 15 mm).

#### Discontinuation of treatment in absence of objective progression of disease

Early death is defined as having no repeat tumor assessments following initiation of study therapy resulting from death of the patient due to disease or treatment. Patients with global deterioration of health status requiring discontinuation of treatment without objective evidence of disease progression will be recorded as “symptomatic deterioration.” This is a reason for stopping therapy, but is NOT objective progressive disease. Every effort will be made to document objective progression even after discontinuation of treatment.

Special Considerations regarding lesion measurability:

**Bone lesions:**

- Bone scan, PET scan, or plain films are not considered adequate imaging techniques to measure bone lesions. However, these techniques can be used to confirm the presence or disappearance of bone lesions.
- Lytic bone lesions or mixed lytic-blastic lesions, with identifiable soft tissue components, that can be evaluated by cross sectional imaging techniques such as CT or MRI can be considered as measurable lesions if the soft tissue component meets the definition of measurability described by RECIST v1.1.
- Blastic bone lesions are non-measurable.

**Cystic lesions:**

- Lesions that meet the criteria for radiographically defined simple cysts should not be considered as malignant lesions (neither measurable nor non-measurable) since they are, by definition, simple cysts.
- “Cystic lesions” though to represent cystic metastases can be considered measurable lesions if they meet the definition of measurability described by RECIST v1.1. However, if non-cystic lesions are present in the same patient, these are preferred for selection as target lesions.

**Lesions with prior local treatment:**

- Tumor lesions situated in a previously irradiated area, or in an area subjected to other local-regional therapy, may be considered measurable ONLY if there is documented progression in that lesion.

**Clinical lesions:**

- Clinical lesions (e.g. biopsy confirmed skin metastasis) will only be considered measurable when they are superficial and larger than 10mm in longest diameter. For the case of skin lesions, documentation by serial color photography using a ruler to measure the size of the lesion is suggested. However, if non-clinical lesions are present in the same patient, these are preferred for selection as target lesions.

**Lesions that spit or coalesce on treatment:**

- When non-nodal lesions “fragment,” the longest diameters of the fragmented portions should be added together to calculate the total lesion sum. Similarly, as lesions coalesce, a plane between them may be maintained that would aid in obtaining maximal diameter measurements of each individual lesion. If lesions have coalesced such that they are no longer separable, the vector of the longest diameter in this instance should be the maximal longest diameter for the “coalesced lesion.”

#### **Lesions which become too small to measure:**

- If the radiologist is able to provide an actual measurement, that should be recorded, even if below 5 mm.
- However, when a lesion becomes difficult to assign an exact measurement, then:
  - If it is the opinion of the radiologist that the lesion has likely disappeared, the measurement should be recorded as 0.
  - If the lesion (including lymph nodes) is believed to be present and is faintly seen, but too small to characterize, a default value of 5mm should be assigned.

#### **Non-measurable lesions:**

- The following are considered non-measurable lesions:
  - Small lesions with longest diameter <10mm or pathologic lymph nodes with  $\geq 10$  to < 15 mm short axis
  - Leptomeningeal disease
  - Ascites
  - Pleural or pericardial effusion
  - Lymphangitic involvement of skin or lung
  - Abdominal masses/organomegaly identified by physical exam that is not measurable by reproducible imaging techniques

#### **Special Considerations for New Lesions:**

The appearance of new malignant lesions denotes disease progression if the longest diameter is at least 10 mm (except for pathological lymph nodes which must have a short axis of at least 15 mm). New lesions may be defined by any modality (i.e. CT, PET, MRI, clinical exam). The finding of a new lesion should be unequivocal (i.e. not attributable to differences in scanning technique, change in imaging modality, or findings thought to possibly represent something other than tumor [e.g. pneumonitis or a “new” bone lesion that may simply be healing or flare or a pre-existing lesion]). This is particularly important when the patient’s baseline lesions show partial or complete response.

A lesion identified on a follow-up study in an anatomical location that was not scanned at baseline is considered to be a new lesion and will constitute progression.

If a new lesion is equivocal, for example because of small size or indeterminate etiology, therapy may be continued and follow-up examination will clarify if it represents new disease. If repeat scans confirm that the new lesion represented malignant disease, the progression should be declared using the date of the initial scan.

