All measurements should be recorded in millimeters. A sum of the diameters (longest for non-nodal lesions, short axis for nodal lesions) for all target lesions will be calculated and reported as baseline sum diameters. If lymph nodes are to be included in the sum, then only the short axis is added into the sum. The baseline sum diameters will be used as reference to further characterize any objective tumor regression in the measurable dimension of the disease.

Non-Target Lesions:

All other lesions (or sites of disease) including pathological lymph nodes should be identified as non-target lesions and should be also recorded at baseline. Measurements are not required and these lesions should be followed as “present,” “absent,” or in rare cases “unequivocal progression.” In addition, it is possible to record multiple non-target lesions involving the same organ as a single item (e.g. “multiple enlarged pelvic lymph nodes”).

Tumor Response Evaluation:

Definitions of response in target and non-target lesions are described in Table 12.1 and 12.2 below. Table 12.3 provides overall responses for all possible combinations of tumor responses in target and non-target lesions.

Table 12.1: Evaluation of target lesions	
Complete Response (CR):	Disappearance of all target lesions
Partial response (PR)	At least a 30% decrease in the sum of the diameters of the target lesions
Progressive disease (PD):	At least a 20% increase in the sum of the diameter of the target lesions or the appearance of one or more new lesions
Stable disease (SD):	Neither sufficient shrinkage to qualify for PR nor sufficient increase to qualify for PD

Table 12.2: Evaluation of non-target lesions	
Complete Response (CR):	Disappearance of all non-target lesions
Incomplete response/Stable disease (SD):	Persistence of one or more non-target lesions
Progressive disease (PD):	Appearance of one or more new lesion and/or unequivocal progression of existing non-target lesion

Table 12.3: Combinations of responses			
Target lesions	Non-target lesions	New lesions	Overall response
CR	CR	No	CR
CR	Incomplete/SD	No	PR
PR	Non-PD	No	PR
SD	Non-PD	No	SD
PD	Any	Yes or No	PD
Any	PD	Yes or No	PD
Any	Any	Yes	PD

Evaluation of Non-Target Lesions:

Although some non-target lesions may actually be measurable, they need not be measured and instead should be assessed only qualitatively at the time points specified in the protocol.

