**Complete Response (CR):** Disappearance of all non-target lesions. All lymph nodes must be non-pathological in size (< 10 mm short axis).

**Non-CR/Non-PD:** Persistence of one or more non-target lesion(s) above the normal limits.

**Progressive Disease (PD):** Unequivocal progression of existing non-target lesions (Note: the appearance of one or more new lesions is also considered progression). To achieve ‘unequivocal progression’ on the basis of the non-target disease, there must be an overall level of substantial worsening in non-target disease such that, even in presence of SD or PR in target disease, the overall tumor burden has increased sufficiently to merit discontinuation of therapy. A modest ‘increase’ in the size of one or more non-target lesions is usually not sufficient to qualify for unequivocal progression status.

Confirmation of Scans

**Verification of Response:** Initial observations of response will be confirmed by repeat scans which should be performed no earlier than 4 weeks after the original observation to ensure that responses identified are not the result of measurement error. After an initial PR or CR is noted, the subsequent protocol-specified tumor assessment may serve as the confirmation.

**Verification of Progression:** Progression of disease should be verified in cases where progression is equivocal. If repeat scans confirm PD, then progression should be declared using the date

of the initial scan. If repeat scans do not confirm PD, then the subject is considered not to have progressive disease per RECIST 1.1.

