### Definitions

Evaluation of best overall response: The best overall response is the best response recorded from the start of treatment until disease progression, as defined in Table 12.3.

Evaluable for toxicity: All patients who receive at least one dose of study therapy will be evaluable for toxicity which will be assessed according to CTCAE v4.0 as well as by documentation of dose delay/adjustments that are required.

Evaluable for objective response: All patients who receive at least one dose of study therapy will be included in the modified intent-to-treat analysis of efficacy. Patients who come off study for any reason prior to the first radiographic tumor assessment will be treated as having progressive disease.

Evaluable for primary/secondary objectives: In order to be considered eligible for the primary and secondary objectives described in this study, patients must receive (1) at least one dose of study therapy and remain on study until at least the first radiographic tumor assessment (week 6) or (2) at least one dose of study therapy and have clear clinical or radiographic progression prior to the planned first radiographic tumor assessment at week 6. Patients who come off study for reasons other than clinical/radiographic progression prior to the first radiographic tumor assessment will be replaced.

Progression free survival (PFS) is defined as the duration of time from beginning study therapy (C1D1) to time of progression or death, whichever occurs first. Clinical deterioration consistent with progressive disease in absence of radiographic evidence of progression (“clinical progression”) will be considered progression for purposes of determining PFS. In patients who continue on study therapy after an initial scan demonstrates progressive disease, if repeat scans confirm PD, then progression should be declared using the date of the initial scan. If repeat scans do not confirm PD, then the subject will not be considered to have progression at the initial scan. Patients who enroll but do not receive any study therapy will not be included in the PFS analysis. Patients who started a

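### A new malignant lesion below 10 mm (node below 15 mm) is progression under Tables 12.1–12.3 but not under the new-lesion paragraph of Section 12.1, and no text says which rule prevails

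*Combined protocol and SAP*

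**What the plan says.** All of the text is in Section 12.1 of the combined protocol and SAP, except where stated.

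**No size limit.** Table 12.1 defines progression as "At least a 20% increase in the sum of the diameter of the target lesions or the appearance of one or more new lesions". Table 12.2 also counts a new lesion as progression, and Table 12.3 scores any combination with a new lesion as overall PD. The text on non-target lesions adds that "the appearance of one or more new lesions is also considered progression".

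**Size limit.** Special Considerations for New Lesions opens: "The appearance of new malignant lesions denotes disease progression if the longest diameter is at least 10 mm". For pathological nodes the requirement is a short axis of at least 15 mm.

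**Two rules in that same subsection carry no limit.** A lesion found in an area not imaged at baseline "is considered to be a new lesion and will constitute progression". For a lesion that is equivocal, with small size given as an example, treatment may continue: "If repeat scans confirm that the new lesion represented malignant disease, the progression should be declared using the date of the initial scan".

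**How response uses these rules.** Definitions states: "The best overall response is the best response recorded from the start of treatment until disease progression, as defined in Table 12.3". Best Overall Response restricts the designation to the period "between the date of first treatment and the date of objectively documented progression per RECIST v1.1" or the start of later therapy, if earlier. Responses must be confirmed on a later scan. Section 14.0 groups patients as responders or non-responders for all three primary objectives and the secondary objective. It mentions Cox regression of PFS as an option.

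**The concern.** An unequivocal malignant lesion of 7 mm, or a new node of 12 mm short axis, is progression when first seen under the tables. Under the first sentence of the new-lesion subsection it is not yet progression. The node example is a sharp one, because the protocol's own list of non-measurable lesions calls nodes of 10 to under 15 mm pathologic.

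This decides who is a responder. Responder status is the grouping variable for the mutation-burden comparison, the neoantigen comparison, the T-cell trajectories and the ligand-expression analysis, and it is the numerator of the response rates by burden group. It also sets the PFS date. Two people applying the document in good faith could label one patient differently, and with about nine responders expected each label carries weight.

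**Working it through.** The plan states no figure that depends on this rule, so there is nothing to reproduce. The check is a scored case followed by two illustrations.

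**1. One patient scored under both rules.** The measurements are hypothetical. Scans follow the six-week schedule.

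| Week | Target sum vs baseline | New malignant lesion (non-nodal, unequivocal) | Tables 12.1–12.3 | 10 mm limit |
|---|---|---|---|---|
| 6 | −35% | 7 mm | PD | PR |
| 12 | −38% | 8 mm | PD | PR (confirmed) |
| 18 | −40% | 11 mm | PD | PD |

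- Tables: PD at week 6, so a non-responder with a PFS event at week 6.
- Size limit: PR at week 6, confirmed at week 12, so a responder with a PFS event at week 18.
- Difference in PFS: 18 − 6 = 12 weeks.

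Section 14.0 counts CR or PR at any time. That does not reconcile the two, because Table 12.3 returns PD at every scan on which the lesion is present.

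**2. When the rules agree.**
- The lesion is at or above the limit when first seen: PD on the same date under both.
- The lesion is called equivocal and later confirmed malignant: back-dating gives the tables' date.
- The lesion first appears after a PR has been confirmed: a responder under both, so only the PFS date can differ.
- The lesion passes the limit before a PR is confirmed: a non-responder under both, so again only the date can differ.

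Responder status therefore changes only if an unequivocal sub-limit lesion appears before confirmation and stays below the limit until a PR is confirmed.

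**3. Effect of relabelling on the response rate.** Inputs: n = 30 (Section 14.0), and an assumed 9 responders from the roughly 30% response rate in Sections 2.1 and 3.0. Assigning that 30% to the size-limit rule is a convenience. Exact limits are the 0.025 quantile of Beta(x, n − x + 1) and the 0.975 quantile of Beta(x + 1, n − x).

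| Case | x/n | Rate | Exact 95% CI |
|---|---|---|---|
| All patients, none relabelled | 9/30 | 30.0% | 14.7–49.4 |
| All patients, one relabelled | 8/30 | 26.7% | 12.3–45.9 |
| Burden group of 15, none relabelled | 6/15 | 40.0% | 16.3–67.7 |
| Burden group of 15, one relabelled | 5/15 | 33.3% | 11.8–61.6 |

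The group size of 15 and its 6 responders are also assumptions.

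**4. Effect on the PFS date.** Assume a lesion first seen at week 6, steady growth, and scheduled six-weekly scans only. Delay = week at which 10 mm is reached − 6.

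| First size | +1 mm per 6 weeks | +2 mm | +3 mm |
|---|---|---|---|
| 5 mm | 36 − 6 = 30 weeks | 24 − 6 = 18 | 18 − 6 = 12 |
| 7 mm | 24 − 6 = 18 | 18 − 6 = 12 | 12 − 6 = 6 |
| 9 mm | 12 − 6 = 6 | 12 − 6 = 6 | 12 − 6 = 6 |

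A lesion that never reaches the limit gives no event from this source.

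**The case against.** **The specific rule refines the general tables.** This is the strongest reply. The special-considerations text qualifies the tables elsewhere: new effusions are not automatically progression, and a new lesion must be unequivocal. A size limit could be one more refinement, and designated readers could apply it uniformly. The reading is possible, but the document does not state it. It sits badly with Definitions, which points best overall response to Table 12.3, and with the subsection's own unscanned-area and back-dating rules, which carry no size limit.

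**Most cases are already handled.** This stands. The equivocal-lesion rule leaves only unequivocal sub-limit lesions in dispute.

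**The tables' PD might be reversed.** This stands as a condition. For patients treated past a first PD, Definitions withdraws the progression if repeat scans do not confirm it. If confirming means the further 10% growth described in Section 9.1, a small new lesion lies outside the measured sum, and with shrinking targets PD might not be confirmed. The non-responder label under the tables holds only if that does not happen.

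**Stronger readings that the text does not support.**
- A reader might take the immune-related criteria as stating the no-limit rule. They say "New lesions do not automatically denote disease progression", listed as a departure from the RECIST method. That supports the no-limit reading by implication only, and it is also compatible with automatic PD from 10 mm.
- A reader might infer from the text on new lesions that are non-measurable at initial progression (Section 9.1, repeated in Section 12.1) that a small new lesion itself triggered PD. The text does not say so; target growth or a larger lesion may have been the cause.
- A reader might infer a minimum PFS shift of one scan interval, 12 weeks after week 48. Section 9.1 allows additional scans at the physician's discretion, so there is no such minimum.

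**Conclusion.** The contradiction is in the current text and is wrong as written: two incompatible rules for one endpoint component, with no order of precedence. Its reach is narrow, being confined to new lesions that are unequivocally malignant and below 10 mm (node 15 mm). For such a patient with targets in PR, responder status can flip, subject to the repeat-scan rule, and the PFS event comes later or not at all.

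The documents give no frequency for these lesions, so the effect may be zero. Under the assumptions shown, one relabelled patient in 30 costs 30.0 − 26.7 = 3.3 percentage points, and the intervals overlap almost entirely. The PFS shifts of 6 to 30 weeks rest on assumed growth and scheduled scans. Section 14.0 describes the study as exploratory and the Cox analysis as optional. Severity: minor.

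**What to change.** In the first sentence of Special Considerations for New Lesions, delete the 10 mm and 15 mm limits, so that an unequivocal new malignant lesion of any size is PD on the date first seen, as in Tables 12.1–12.3. Leave lesions too small to judge to the existing equivocal-lesion paragraph. Keep the 10/15 mm limits where they define what enters the further-progression sum (Section 9.1, Treatment beyond Disease Progression; Section 12.1, Continuation of treatment despite radiographic progressive disease).

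If the sponsor prefers a size limit, it should be added to Tables 12.1–12.3 and the non-target text, with PD dated at the scan where the limit is reached. Either choice should be made before responses are read.

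The cost of the preferred option is one sentence, with no extra scans or data. Its downside is that a patient with shrinking targets and a small unequivocal new lesion counts as a RECIST non-responder, although irPR remains available. That patient must also meet the Section 9.1 criteria for treatment beyond progression, including written consent, to stay on treatment.

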### Special Considerations for Pleural/Pericardial Effusions and Ascites:

As above, pleural/pericardial effusions and ascites are considered non-measurable lesions. The appearance of new or worsening pleural/pericardial effusions or ascites does not necessarily constitute unequivocal progression unless cytologically proven to be of malignant origin since some effusions may be a therapy-related toxicity or related to other medical conditions.

If a new or worsening pleural/pericardial effusion or ascites is determined to be unequivocally related to progressive disease (e.g. cytopathologic confirmation of new effusion or change from “trace” to “large” effusion), then this is consistent with progression and treatment would be discontinued.

If a new or worsening pleural/pericardial effusion or ascites is equivocal, for example because of small size or indeterminate etiology, therapy may be continued and follow-up examination or cytopathologic analysis will clarify if it represents new disease. If repeat scans or procedures confirm that the new lesion represented malignant disease, the progression should be declared using the date of the initial scan.

